3.2.17 Pooling of Centres

Two countries (one centre for each) are planned to be involved: Netherlands and United Kingdom.

3.2.18 Interim analysis

No formal preliminary or interim analyses are planned for this study. If an unplanned preliminary or interim analysis is deemed necessary, the Sponsor clinical pharmacologist or Investigator will consult with the appropriate medical director or designee to determine if it is necessary to amend the protocol.

Blood lead concentrations from screening and baseline (Day-1) will be obtained on an ongoing basis to verify that these values are within the 95% confidence interval of the mean blood lead concentration of 31,4µg/l used in the determination of sample size (see Section 8.1.2) and therefore confirm the assumptions for sample size calculation. If not, the sample size might be re-evaluated accordingly.

3.2.19 Role of data review committee (DRC)

No independent data monitoring committee/interim data review committee will be used in this study.

3.2.20 Covariates and analysis of subgroups

No covariates or analysis of subgroups are planned in this study.

Nevertheless, analyses by country (Netherlands and United Kingdom) will be presented for demographic and baseline characteristics and also for blood lead concentrations.

4 COMPUTER SYSTEMS, SOFTWARE AND VALIDATION OF PROGRAMS

4.1 Hardware

The statistical analysis will be performed using PC on a Windows 7 operating system.

4.2 Software

All tables, figures and listings (TFLs) will be produced and statistical analysis performed using statistical analysis system (SAS®) version 9.4 [2]. All outputs will be provided as individual word files following GEN014 template and compiled in bookmarked .pdf files as per ICH section (e.g. 14.1, 14.2 ...).

4.3 Validation programs

Biostatistical Biometrics will provide a validation plan to Ipsen identifying the methods of validation.

The study statistician is responsible for reviewing each output associated with the deliverable product. Program logs are checked by the statistical programmer for logical, syntax and fatal errors. The checks in SAS includes, but is not limited to, all ERRORS, WARNINGS, BY-VALUE merge messages, NOTES, and UNINITIALIZED variables. Program logs are also reviewed for accurate and consistent variable and observation counts following each procedure and data step.

The study statistician is responsible for checking and reviewing the work produced using whatever method he/she feels is appropriate (e.g. SAS code review, hand calculation, etc.) to reassure of the quality of the output.

Outputs are reviewed for typographical errors, misspellings and nonsensical values or results and to check the consistency with the statistical analysis plan. Outputs are cross-checked against each other for accuracy and consistency. For statistical tables, listings, appendix listings, and figures, this procedure includes comparison of subject group numbers, counts of subjects at each observation point, and consistency of results for variables between outputs.

Findings of the quality control reviews are communicated to the party responsible for making necessary changes. The programs will be retested after modifications.

After final review, and when no further change is required to produce the deliverable, the statistical programmer and the study statistician have to complete and sign the quality control and statistical analysis results follow-up's validation checklist, to indicate that they have successfully performed all of their responsibilities. Copies of the internal quality control forms produced for the validation process will be provided to the sponsor to support the validation.

4.4 Restitution of the programs

All programs (including macros and analysis datasets) producing the tables, listings and statistical outputs along with associated logs should be given to the sponsor when the TFLs and statistical analyses have been finalised.

5 CHANGES FROM PROTOCOL

Changes from the final protocol dated 7 September 2016 are the following:

Results of plasma samples will not be analysed during the study therefore will not be included in the clinical study report neither the biobanking blood samples of other elemental impurities that may be dosed after the study upon need or request from Health Agencies.

Since there was no eligibility criterion on blood lead level at study entry, some dosages could evidence an unexpected elevated level at baseline.

In the protocol, hypothesis for sample size calculation was based on the mean value in literature data in France (Falq et al. 2011).

In case of high blood level of lead at one or two of the baseline points, a sensitivity analysis may be performed.

This analysis will exclude the patients with such unexpected baseline results to avoid any confounding of the mean study results.

7 APPENDICES TO THE SAP TEMPLATE

Appendix 1: Derived Data

The following derived data will be calculated:

(1) Study day

Study day will be defined as ‘-1’ for the day prior to IMP administration and as ‘1’ for the day of IMP administration (i.e. day 0 does not exist).

(2) Study duration

Study duration (weeks) will be calculated as [(last visit attended - date of first IMP administration) + 1] / 7.

(3) Study drug exposure

Study drug exposure (weeks) will be derived using information from diary and will be calculated as [(last date of IMP administration - first date of IMP administration) + 1] / 7.

(4) Compliance

Compliance (%) will be calculated as (the total number of sachets taken / the total number of expected sachets to be taken) x 100.

The total number of sachets taken will be derived using information from diary as the sum of number of sachets taken when a date of IMP administration is entered.

The total number of expected sachets to be taken will be derived using information from diary based on three sachets per day (TID) (morning, noon, and evening) to be taken by the subject as [(last date of IMP administration - first date of IMP administration) + 1] x 3.

(5) Baseline

BLL baseline will be derived as the average between the available screening and pre-dose (Day-1) values.

Baseline for other parameters will be derived as the last available (and reliable if applicable) assessment before IMP administration.

(6) Absolute change from baseline

Absolute change from baseline will be calculated as the difference from baseline (e.g. assessment at the visit – assessment at baseline).

(7) Ae parameter

Ae parameter (ng) will be calculated as the cumulated concentration of EI in urine × the total volume of urine collected over 24 hours.

(8) Therapeutic Class

The therapeutic class will correspond to the first 3 digits of the ATC code. The decoding of the therapeutic class will be done from the WHO-DD June 2016 Version or higher.

(9) Prior and concomitant medication duration

If the start and end dates of the medication are identical then “<1” day will be presented with the duration in hh:mm recorded in the eCRF if it is available. If times are available, the duration of concomitant treatments will be calculated as (end date/time - start date/time). If at least one time is missing, the duration of concomitant treatments will be calculated as (end date - start date) + 1. If the recorded end date is continuing at the end of the study then the end date will be listed as “ongoing” and the duration will be approximated as “≥(last attended visit date –

start date) + 1” day(s). If the start date or the end date are partial, the duration will be presented as an inequality “≥xx” day(s) [i.e. ≥2 where start date=2004-01-31 and end date=2004-02 or start date=2004-01 and end date=2004-02-01] but if both are partial or one is missing the duration will not be presented.

(10) AE duration

If the start and end dates of the AE are identical then “<1” day will be presented with the duration in hh:mm recorded in the eCRF if it is available. If times are available, the duration will be calculated as (end date/time – start date/time) and presented in days hh:mm. If at least one time is missing and if the duration is greater than 24 hours then it will be calculated as (end date - start date) + 1 and presented in days. If the recorded end date is continuing at the end of the study, the end date will be listed as “ongoing” and the duration will be approximated as “≥(last attended visit date – start date) + 1” day(s). If the start date or the end date are partial the duration will be presented as a superior inequality “≥xx” day(s) [i.e. ≥2 where start date=2004-01-31 and end date=2004-02 or start date=2004-01 and end date=2004-02-01].

(11) Time since last dose for adverse event

If the start date of the adverse event is identical to the date of last administration, then “<1” day will be presented with the time to onset in hh:mm recorded in the eCRF if it is available. If times are available, the time will be calculated as (start date/time – last administration date/time) and presented in days hh:mm. If at least one time is missing and if the time to onset is greater than 24 hours then it will be calculated as (start date - last administration date)+1 and presented in days. If the start date and the associated information do not allow to state about the last dose received (partial start date or start at administration day without knowing if it started before or after the drug intake), all the possible time since last dose will be presented [i.e.: if a subject received a daily administration and reported an AE at second administration day but without indication about before or after the drug intake the time since last dose will be as “2 / <1”]. If the start date is partial, the time since last dose will be presented as an superior inequality (i.e.: for an AE started in 2004-02 after the only administration performed on 2004-01-31, the time since last dose will be as “≥2” days). If the start date is missing the time since last dose will not be presented although the AE will be assigned to each dose received before its end date.

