3.3.1.3 Treatment Period

The treatment period will occur from Day 1 (first intake in the morning) to Day 35 (last intake in the evening) and subjects will be required to attend the CRU on several occasions during the treatment period:

- Day 1 (Visit 2): The subjects will be dosed within the unit with Smecta® at breakfast, lunch and dinner time, PK samples will be collected as described in the Schedule of events (see Attachment #1_Section 15.1) and the subject will leave the unit on Day 2 after PK sampling and Smecta® administration in the morning. Subjects will receive a box containing Smecta® treatment for a bit more than 2 weeks (20 days) as well as a diary to record the drug administration and consistency and frequency of stools at the day before the Day 8 visit.
- Out-patient visits (Visits 3 to 6): the subjects will be required to come back to the CRU for out-patient visits on Days 8, 15, 22 and 29 for blood sampling for impurities dosing and the review of adverse events and concomitant medication. One day before Day 8, subject will need to complete the diary with assessment of consistency and frequency of stools using the Bristol scale. During those visits, stools will be collected only on Day 8. At Day 22 the subjects will receive a second box containing Smecta® treatment for the last 2 weeks.
- Days 35-36 (Visit 7): Subjects will come back to the CRU in the morning of Day 35 (or the evening before for convenience) in order to start the process to collect urine samples, blood and stools sampling. They will be dosed with Smecta® at breakfast,

lunch and dinner. They will leave the unit in the morning of Day 36 after the completion of the 24-hour urine collection and PK sample in the morning.

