7.6 Compliance to Study Procedures

7.6.1 Compliance to Protocol

Every attempt will be made to select subjects who have the ability to understand and comply with instructions. Noncompliant subjects may be discontinued from the study. The time and day of drug administration will be recorded by the study site when present at the clinical unit and by the subject when self-administered (using Subject Diary). These will be recorded in the eCRF by the site. Drug accountability records will be maintained by the study site.

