3.2.9 Subject compliance

The time and day of drug administration will be recorded by the study site when present at the clinical unit and by the subject when self-administered using a diary.

Compliance to diosmectite (Smecta®) intake will be based on this diary.

All treatment administration information will be listed by subject, timepoint and date of administration on the safety population.

Three listings will be performed: one for the treatments taken, one for the meals taken, and one for the drug accountability.

Study drug exposure (as defined in [Appendix 1 \(3\)](#)) in weeks will be summarized.

A summary table will present the global compliance (expressed in percentage as defined in [Appendix 1 \(4\)](#)) on the treatment period for the safety population.

Additionally, compliance will be categorized as follows: < 80% (Under compliance), 80-120% (Compliance) and > 120% (Over compliance) and will be summarized.

In the included population, protocol deviations from observed and scheduled times will be presented with the reasons for exclusion from the PP population.

All the protocol deviations identified will be also listed by subject with the reasons for exclusion.

A protocol deviation specification document will be provided further by Aepodia.

3.2.10 *Prior and concomitant medications*

Concomitant medication will be coded by using the World Health Organisation – Drug Dictionary (WHO-DD) June 2016 Version or higher.

The therapeutic class will correspond to the second level of anatomic therapeutic class (ATC) code, that is, corresponding to the first 3 figures.

The date and time of baseline (Smecta® on Day 1) will be used as the cut-off date for the definition of prior and concomitant medications:

A prior medication will be defined as a medication stopped prior to the date of baseline.

A concomitant medication will be defined as a medication which is taken by subject any time during the study after the date of baseline.

A medication that started before the date of baseline and is continuing after will be considered as both, prior and concomitant.

Prior, concomitant and both prior and concomitant medications will be flagged P, C and PC respectively, in all listings.

Listings will be presented for the therapeutic class, preferred name and reported name on the safety population. The listings will be sorted by subject, chronological start date, therapeutic class, preferred name and reported name.

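### SAP 3.2.9 and Appendix 1 (3)–(4) derive drug exposure and compliance from the subject diary alone, although doses given in the unit are recorded by the site

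*SAP*

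**What the plan says.** SAP section 3.2.9 states who records each administration: it is "recorded by the study site when present at the clinical unit and by the subject when self-administered using a diary". Protocol section 7.6.1 makes the same split and has the site enter both kinds of record in the eCRF.

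SAP section 3.2.9 then narrows the source: "Compliance to diosmectite (Smecta®) intake will be based on this diary". Appendix 1 keeps to that source. Item (3) reads "Study drug exposure (weeks) will be derived using information from diary", with weeks counted from the first to the last administration date inclusive. Item (4) reads "The total number of sachets taken will be derived using information from diary". Its denominator, the expected sachets, also comes from the diary, at three per day between the first and last administration dates. Neither item names another source.

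Protocol section 3.3.1.3 places the following doses in the unit: all three on Day 1, the morning dose on Day 2 before discharge, and all three on Day 35. In the text on the visit that ends on Day 2, the same section says subjects receive their take-home box "as well as a diary to record the drug administration". Protocol section 5.1.2 is looser about recording. It has the subject enter all intakes in the diary, or the site enter them in the eCRF where that applies.

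**The concern.** The SAP describes two sources of dosing data and then builds its exposure and compliance variables on one of them. The source left out covers the supervised doses, which are the best documented in the study and include the first and the last of the course. A programmer who follows the text would therefore start exposure at the first diary entry and end it at the last, and would count only sachets taken at home.

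At stake is Table 14.1.12, the planned summary of how much of the five-week course subjects received, together with the compliance listing behind it (16.2.5.4). A systematic shortfall there would also disagree with Listing 16.2.5.1, which is meant to show every administration.

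**Working it through.** **Inputs**

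- Course: Day 1 morning to Day 35 evening, three sachets a day (protocol 3.3.1.3), so 35 × 3 = 105.
- In-unit doses (protocol 3.3.1.3): 3 (Day 1) + 1 (Day 2 morning) + 3 (Day 35) = 7, or 7/105 = 6.7%.
- Home doses: 2 (Day 2 noon and evening) + 32 days × 3 (Days 3 to 34) = 98. Check: 98 + 7 = 105.
- Formulas (SAP Appendix 1): exposure = (last date − first date + 1)/7; expected sachets = (last date − first date + 1) × 3; compliance = taken/expected × 100.
- Compliance bands (SAP 3.2.9): below 80%, 80–120%, above 120%.

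**Step 1. Reproduce the planned duration from all records.** Exposure = (35 − 1 + 1)/7 = 5.00 weeks. Compliance = 105/105 = 100%. This agrees with the planned five weeks.

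**Step 2. Apply the rule as written to a fully adherent subject whose in-unit doses are not in the diary.** The first diary date is Day 2 and the last is Day 34.

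| Quantity | All records | Diary only |
|---|---|---|
| Sachets taken | 105 | 98 |
| Sachets expected | 105 | (34 − 2 + 1) × 3 = 99 |
| Compliance | 100% | 98/99 = 99.0% |
| Exposure (weeks) | 5.00 | 33/7 = 4.71 |

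Exposure is short by 2 days in 35, or 5.7%. Compliance moves by only about one point, because the numerator loses 7 and the denominator loses 6.

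**Step 3. Look at the 80% limit.** Let h be the home doses taken, with all seven in-unit doses taken and the diary still running from Day 2 to Day 34. True compliance is (h + 7)/105 and reported compliance is h/99. The true value is at least 80% when h ≥ 77. The reported value is below 80% when h < 79.2. The two disagree for three values of h:

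| h | Total taken | True | Reported |
|---|---|---|---|
| 77 | 84 | 80.0% | 77.8% |
| 78 | 85 | 81.0% | 78.8% |
| 79 | 86 | 81.9% | 79.8% |

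**Step 4. A treated subject with no home dose.** Someone who stops before noon on Day 2 is in the Safety population but has no diary date. Exposure cannot be computed and compliance is 0/0.

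**Step 5. Does the Day 35 window change this?** Protocol 7.3.1 lets the visit fall a day earlier or later, with dosing adjusted to match. At Day 36 the diary gives 34/7 = 4.86 weeks against a true 36/7 = 5.14. At Day 34 it gives 32/7 = 4.57 against 34/7 = 4.86. The shortfall is two days each time.

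Seven is a nominal count. Protocol 3.3.1.3 allows arrival the evening before Day 35. If that evening's dose were given in the unit, the diary would hold 97 sachets, 97/99 = 98.0%, and exposure would stay at 4.71 weeks. Footnote a of the schedule also shows an intake on the morning of Day 36, which conflicts with a last intake on the evening of Day 35. Those passages need to be reconciled.

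**The case against.** The best case against the point is that the wording is loose and the method is sound. SAP section 3.2.15 defines derived data as computed from eCRF raw data, and both the site's and the subject's dosing records go into the eCRF. Appendix 1 (1) sets Day 1 as the day of first administration, and Appendix 1 (2) uses the date of first administration without tying it to the diary. A first dose date of Day 2 would sit badly with both. A sensible programmer might merge the sources unprompted. That is plausible, but items (3) and (4) name the diary and nothing in the SAP overrides them.

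It is also fair to say that misclassification at the 80% limit would be rare. It needs 19 to 21 missed home sachets with every in-unit dose taken. Protocol section 6.1 also has a missed dose taken together with the next one, which preserves the sachet count.

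A reader might infer more than the documents support, in three ways:

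- **That in-unit doses cannot be in the diary, so no subject can show five weeks.** Protocol 3.3.1.3 does not say the diary is handed out only at discharge on Day 2, subjects already hold it by Day 35, and protocol 5.1.2 leaves room for every intake to be entered.
- **That a full complier would show 98/105 = 93.3%, with a wider band of subjects mislabelled.** That needs true dose dates in the denominator and diary sachets in the numerator. Appendix 1 (4) takes both from the diary.
- **That the blood-lead result or the Per Protocol set is affected.** SAP section 2.6 defines that set by completion and absence of major deviations and gives no compliance threshold. The blood-lead summaries in SAP section 3.2.2.1 do not use exposure or compliance.

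**Conclusion.** The point holds as a minor one. It is a stated derivation that gives a wrong number if followed, and so more than a missing detail. The firmer error is in exposure; for a full complier the compliance error is about one percentage point.

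This rests on three assumptions: in-unit doses are not also written in the diary, all home doses are, and the nominal visit days are kept. If sites had subjects enter in-unit doses as well, the discrepancy disappears, but the SAP does not require that.

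The consequence is confined to descriptive outputs. Dosing can still be checked in Listings 16.2.5.1 (administration) and 16.2.5.3 (accountability). One thing remains open: SAP section 3.2.9 defers protocol deviations to a separate specification still to come. If that document were to use the compliance percentage, the error would carry over into it. Nothing in the present documents says that it will.

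**What to change.** In SAP Appendix 1 (3) and (4), replace the diary as sole source with all IMP administration records in the eCRF, meaning site-recorded doses in the unit plus diary-recorded home doses. Apply this to the first and last dose dates, and so to expected sachets, and to sachets taken. Change the matching sentence in SAP section 3.2.9 to name both sources.

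Where both sources hold the same dosing occasion, count it once. Keep the number of sachets recorded for that occasion, so that a missed dose taken with the next one is not lost in de-duplication.

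A full complier then shows 5.00 weeks and 105/105 = 100%, and a subject with in-unit doses only has computable values. The cost is a few words in two places and one merge of records that the eCRF already holds and Listing 16.2.5.1 already needs. No new data and no protocol amendment are required.

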Appendix 2: List of TFLs

Listings index

16.1.7 Randomisation Scheme and Codes

Not applicable

16.2 SUBJECT DATA LISTINGS

16.2.1 Discontinued subjects

- Listing 16.2.1.1: Subject Disposition – Screened Population
- Listing 16.2.1.2: Subject Disposition – Study Withdrawals – Screened Population
- Listing 16.2.1.3.1: Inclusion Criteria Assessments
- Listing 16.2.1.3.2: Inclusion Criteria not Met – Included Population
- Listing 16.2.1.4.1: Exclusion Criteria Assessments
- Listing 16.2.1.4.2: Exclusion Criteria not Met – Included Population
- Listing 16.2.1.5: Assessments Dates – Included Population
- Listing 16.2.1.6: Re-enrollment of Subjects – Included Population

